7.1 Adverse Events and Potential Risks

7.1.1 Isosulfan Blue (Lymphazurin) 1%

- hypersensitivity reactions - approximately 2% of patients
- blue discoloration of the skin
- No drug interactions are known [38].

7.1.2 Indocyanine Green

- anaphylactic or urticarial reactions in patients with a history of iodine allergy

7.2 Definitions

7.2.1 Adverse Events

An **adverse event** (AE) is any unfavorable or unintended event, physical or psychological, associated with a research study, which causes harm or injury to a research participant as a result of the participant's involvement in a research study. The event can include abnormal laboratory findings, symptoms, or disease associated with the research study. The event does not necessarily have to have a causal relationship with the research, any risk associated with the research, the research intervention, or the research assessments.

Adverse events may be the result of the interventions and interactions used in the research; the collection of identifiable private information in the research; an underlying disease, disorder, or condition of the subject; and/or other circumstances unrelated to the research or any underlying disease, disorder, or condition of the subject. In general, adverse events that are at least partially the result of (a) or (b) would be considered related to the research, whereas adverse events solely related to (c) or (d) would be considered unrelated to the research.

External adverse events are adverse events experienced by subjects enrolled in multicenter clinical trials at sites other than the site(s) over which the Institutional Review Board has jurisdiction.

Internal adverse events are adverse events experienced by subjects enrolled at the site(s) under the IRB's jurisdiction for either multicenter or single-center research projects.

7.2.2 The significance of an adverse event is used to describe the patient/event outcome or action criteria associated with events that pose a threat to a patient's life or functioning (i.e., moderate, severe or life threatening). Based on the National Cancer Institute Guidelines for the Cancer Therapy Evaluation Program, severity can be defined by the following grades of events:

Grades 1 are mild adverse events. (e.g., minor event requiring no specific medical intervention; asymptomatic laboratory findings only; marginal clinical relevance)

Grades 2 are moderate adverse events (e.g., minimal intervention; local intervention; non-invasive intervention; transfusion; elective interventional radiological procedure; therapeutic endoscopy or operation).

Grades 3 are severe and undesirable adverse events (e.g., significant symptoms requiring hospitalization or invasive intervention; transfusion; elective interventional radiological procedure; therapeutic endoscopy or operation).

Grades 4 are life threatening or disabling adverse events (e.g., complicated by acute, life-threatening metabolic or cardiovascular complications such as circulatory failure, hemorrhage, sepsis; life-threatening physiologic consequences; need for intensive care or emergent invasive procedure; emergent interventional radiological procedure, therapeutic endoscopy or operation).

Grades 5 are fatal adverse event resulting in death.

7.2.3 Serious Adverse Events

A **serious adverse event** (SAE) is any adverse experience occurring at any dose that results in any of the following outcomes:

- Results in **death**.
- Is a **life-threatening** adverse experience. The term life-threatening in the definition of serious refers to an adverse event in which the subject was at risk of death at the time of the event. It does not refer to an adverse event which hypothetically might have caused death if it were more severe.
- Requires **inpatient hospitalization or prolongation of existing hospitalization**. Any adverse event leading to hospitalization or prolongation of hospitalization will be considered as Serious, UNLESS at least one of the following expectations is met:
 - The admission results in a hospital stay of less than 12 hours OR

- The admission is pre-planned (i.e., elective or scheduled surgery arranged prior to the start of the study) OR
- The admission is not associated with an adverse event (e.g., social hospitalization for purposes of respite care).

However it should be noted that invasive treatment during any hospitalization may fulfill the criteria of “medically important” and as such may be reportable as a serious adverse event dependant on clinical judgment. In addition where local regulatory authorities specifically require a more stringent definition, the local regulation takes precedent.

- Results in **persistent or significant disability/incapacity**. The definition of disability is a substantial disruption of a person’s ability to conduct normal life’s functions.
- Is a **congenital anomaly/birth defect**.
- Is an **important medical event**. Important medical events that may not result death, be life-threatening, or require hospitalization may be considered a serious adverse experience when, based upon appropriate medical judgment, they may jeopardize the patient or subject and may require medical or surgical intervention to prevent one of the outcomes listed in this definition. Examples of such medical events include allergic bronchospasm requiring intensive treatment in an emergency room or at home, blood disease or disorders, or convulsions that do not result in inpatient hospitalization, or the development of drug dependency or drug abuse.

7.2.4 Expectedness

Adverse Events can be Expected or Unexpected.

An expected adverse event is an event previously known or anticipated to result from participation in the research study or any underlying disease, disorder, or condition of the subject. The event is usually listed in the Investigator Brochure, consent form or research protocol.

An unexpected adverse event is an adverse event not previously known or anticipated to result from the research study or any underlying disease, disorder, or condition of the subject.

7.2.5 Attribution

Attribution is the relationship between an adverse event or serious adverse event and the study drug. Attribution will be assigned as follows:

- Definite – The AE is clearly related to the study drug.
- Probable – The AE is likely related to the study drug.
- Possible – The AE may be related to the study drug.
- Unlikely – The AE is doubtfully related to the study drug.
- Unrelated – The AE is clearly NOT related to the study drug.

7.3 Reporting Procedures for All Adverse Events

All participating investigators will assess the occurrence of AEs throughout the subject's participation in the study. Subjects will be followed for toxicity for 30 days after treatment has been discontinued or until death, whichever occurs first. The clinical course of each event will be followed until resolution, stabilization, or until it has been determined that the study treatment or participation is not the cause.

The investigator is responsible for ensuring that all adverse events observed by the investigator or reported by the subject which occur after the subject has signed the informed consent are fully recorded in the subject's case report form, subject's medical records, and/or any other institutional requirement. Source documentation must be available to support all adverse events.

A laboratory test abnormality considered clinically relevant (e.g., causing the subject to withdraw from the study), requiring treatment or causing apparent clinical manifestations, or judged relevant by the investigator, should be reported as an adverse event.

The investigator will provide the following for all adverse events:

- Description of the event
- Date of onset and resolution
- Grade of toxicity
- Attribution of relatedness to the investigational agent
- Action taken as a result of the event
- Outcome of event

In this study, descriptions and grading scales found in the NCI Common Terminology Criteria for Adverse Events (CTCAE) version 4.0 available at <http://ctep.cancer.gov> will be utilized for AE reporting.

Investigative sites will report adverse events to their respective IRB according to the local IRB's policies and procedures in reporting adverse events.

7.4 Serious Adverse Event Reporting Procedures

Serious adverse events that occur beginning with the signing of the informed consent form, during treatment, or within 30 days of the last dose of treatment must be reported to The Cleveland Clinic Principal Investigator.

Investigative sites will report serious adverse events to their respective IRB according to the local IRB's policies and procedures in reporting serious adverse events.

7.5 Data Safety Toxicity Committee

It is the Case Comprehensive Cancer Center's Principal Investigator's responsibility to ensure that ALL serious adverse events are reported to the Case Comprehensive Cancer Center's Data Safety Toxicity Committee. This submission is simultaneous with their submission to the Sponsor or other Regulatory body.

8.0 PHARMACEUTICAL INFORMATION

A list of the adverse events and potential risks associated with the investigational or commercial agents administered in this study can be found in Section 8.0.

8.1 Lymphazurin

- Chemical Name:** N-[4- [[4-(diethylamino)phenyl] (2,5-disulfophenyl) methylene]-2,5- cyclohexadien-1-ylidene]-N-ethylethanaminium hydroxide
- Other Names:** Isosulfan Blue
- Mode of Action:** binds to serum proteins and is picked up by lymphatic vessels
- Metabolism:** 10% is excreted unchanged in the urine in 24 hrs
- Product description:** a sterile aqueous solution for subcutaneous administration. The solution contains no preservative.
- Solution preparation:** Phosphate buffer in sterile, pyrogen free water is added in sufficient quantity to yield a final pH of 6.8-7.4. Each ml of solution contains 10mg Isosulfan blue, 6.6 mg sodium monohydrogen phosphate and 2.7mg potassium dihydrogen phosphate.
- Storage requirements:** none
- Route of administration:** cervical
- Drug Procurement:** Isosulfan Blue must be obtained from commercial sources.

8.2 Indocyanine Gree

- Chemical Name:** sodium 4-[2-[(1E,3E,5E,7Z)-7-[1,1-dimethyl-3-(4-sulfonatobutyl)benzo[e]indol-2-ylidene]hepta-1,3,5-trienyl]-1,1-dimethylbenzo[e]indol-3-ium-3-yl]butane-1-sulfonate
- Other Names:** Cardiogreen, Foxgreen, IC-Green
- Classification:** Cyanine Dye
- Mode of Action:** Peak spectral absorption at about 800 nm and therefore visible in the near infrared spectrum. Requires special camera device to visualize. Binds tightly to plasma proteins and therefore has a propensity for lymphatic tissue

Metabolism: removed by the liver and bile

Product description: A fluorescent dye used in medicine as an indicator substance

Solution preparation: available in a powder form and reconstituted in sterile water

Storage requirements: none

Route of administration: cervical

Drug Procurement: indocyanine green must be obtained from commercial sources.

9.0 STUDY PARAMETERS AND CALENDAR

9.1 Study Parameters

9.1.1 Screening Evaluation

Screening evaluations for inclusion and exclusion criteria will be used to determine the eligibility of each subject for the study. All evaluations must be completed ≤ 30 days prior to administration of protocol therapy.

9.1.2 Study Period

The study begins at the time of pre-operative evaluation and ends at the time of the post-operative visit.

9.2 Calendar

Screening evaluation will be conducted within 1 day prior to administration of protocol therapy.

10.0 MEASUREMENT OF EFFECT

10.1 Sentinel Node Biopsy Evaluation

For the purposes of this study, the success of sentinel node biopsy will be evaluated by the detection rate of the sentinel lymph node for each patient, the sensitivity of the sentinel node to determine the true lymph node status (metastatic disease or not), and the false negative rate. Definitions for these are below. The comparator for these values will be the detection rate, sensitivity, and false negative rate for breast and vulvar cancers, in which sentinel lymph node biopsy is standard practice. In 2005, the American Society of Clinical Oncology stated that for breast cancer, sentinel lymph node detection rate should reach 85% with a false negative rate $\leq 5\%$ [39]. In the most recent randomized trials examining sentinel lymph node biopsy in breast cancer, detection rates ranged from 93-97%. The false negative rates in the SNAC, ALMANAC, and NSABP B-32 trials ranged from 4.7% (ALMANAC) to 9.8% (NSABP B-32) [40, 41, 42]. In vulvar cancer, where sentinel lymph node biopsy has also become more widely accepted, studies similarly report detection rates ranging from 93-98% while false negative rates are approximately 7.7 -8.3% [43,44].

[figure not shown]
10.1.1 Definitions

Sensitivity, false negative and false negative rate will be limited to those patients in whom a sentinel node is detected.

False negative = a sentinel node that is identified and determined to be negative, however, upon complete lymphadenectomy, a different lymph node is found to be positive

Sensitivity = the number of patients with a positive SLN over those patients with a positive SLN plus those patients with a false negative lymph node

False negative rate = 1-sensitivity or the number of patients with a false negative SLN over the number of patients with a positive SLN plus those with a false negative lymph node

	Our definition	Other definition
FN	H	F+H
FN Rate	$H/D+H$	$F+H/D+F+H$
Sensitivity	$D/D+H$	$D/D+F+H$
NPV	I/E	-

11.0 RECORDS TO BE KEPT / REGULATORY CONSIDERATIONS

Adverse event lists, guidelines, and instructions for AE reporting can be found in Section 7.0 (Adverse Events: List and Reporting Requirements).

11.1 Data Reporting

The RedCap Database will be utilized for data collection for both accrual entry and trial data management. RedCap is a Data Management System housed on secure servers maintained at The Cleveland Clini. Access to data through RedCap is restricted by user accounts and assigned roles. Once logged into the RedCap system with a user ID and password, RedCap defines roles for each user which limits access to appropriate data.

RedCap is designed with the capability for study setup, activation, tracking, reporting, data monitoring and review, and eligibility verification.

11.2 Regulatory Considerations

The study will be conducted in compliance with ICH guidelines and with all applicable federal (including 21 CFR parts 56 & 50), state or local laws.

11.2.1 Written Informed consent

Provision of written informed consent must be obtained prior to any study-related procedures. The Principal Investigator will ensure that the subject is given full and adequate oral and written information about the nature, purpose, possible risks and benefits of the study as well as the subject's financial responsibility. Subjects must also be notified that they are free to discontinue from the study at any time. The subject should be given the opportunity to ask questions and allowed time to consider the information provided.

The original, signed written Informed Consent Form must be kept with the Research Chart in conformance with the institution's standard operating procedures. A copy of the signed written Informed Consent Form must be given to the subject.

11.2.2 Subject Data Protection

In accordance with the Health Information Portability and Accountability Act (HIPAA), a subject must sign an authorization to release medical information to the sponsor and/or allow the sponsor, a regulatory authority, or Institutional Review Board access to subject's medical information that includes all hospital records relevant to the study, including subjects' medical history.

11.2.3 Retention of records

The Principal Investigator supervises the retention of all documentation of adverse events, case report forms, source documents, records of study drug receipt and dispensation, and all IRB correspondence for as long as needed to comply with national and international regulations and

the institution in which the study will be conducted, or for the period specified by the sponsor, whichever is longer. No records will be destroyed until the Principal Investigator confirms destruction is permitted.

11.2.4 Audits and inspections

Authorized representatives of the sponsor, a regulatory authority, an Independent Ethics Committee (IEC) or an Institutional Review Board (IRB) may visit the Center to perform audits or inspections, including source data verification. The purpose of an audit or inspection is to systematically and independently examine all study-related activities and documents to determine whether these activities were conducted, and data were recorded, analysed, and accurately reported according to the protocol, Good Clinical Practice (GCP), guidelines of the International Conference on Harmonization (ICH), and any applicable regulatory requirements.

11.2.5 Data Safety and Monitoring Plan

This protocol will adhere to the policies of the Case Comprehensive Cancer Center Data and Safety Monitoring Plan in accordance with NCI regulations.

12.0 STATISTICAL CONSIDERATIONS

Numerical values will be summarized by mean and standard deviation when the data have an approximately normal distribution; otherwise they will be summarized by median and interquartile range. Normality will be evaluated through visual inspection of histograms, boxplots, and normal QQ plots. Analyses specific to each aim are listed below. Secondary multivariable analysis may include logistic regression using metastasis as the dependent variable with type of dy utilized, surgical modality, surgeon, tumor stage, grade and presence of lymphovascular space invasion as independent variables. Significance will be determined by a p-value less than or equal to 0.05 unless otherwise stated.

Specific Aim 1:

Sensitivity, specificity, and negative predictive value of SLN biopsy for detecting metastasis will be estimated and appropriate 95% confidence intervals for each value will be provided.

Specific Aim 2:

Sensitivity, specificity, and negative predictive value of SLN biopsy for detecting metastasis will be compared between surgical modalities using pairwise comparisons for each surgical modality. Comparisons will be performed using two sample tests of proportions based on a normal approximation. Since three such pairwise comparisons are required, significance will be determined by a Bonferonni adjusted significance level of $0.05 / 3 = 0.17$.

Specific Aim 3:

Sensitivity, specificity, and negative predictive value of SLN biopsy for detecting metastasis will be compared between injectants utilized using a two sample test of proportions based on a normal approximation.

Specific Aim 4:

Total operating room time will be estimated as a mean with 95% confidence interval if the data have an approximately normal distribution. Otherwise, the median and a bootstrapped 95% confidence interval for the median will be reported. Similar summaries will be provided for the console time (robotic)/ operating time.

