1.0 INTRODUCTION

1.1 Endometrial Cancer and Treatment

The incidence of endometrial cancer in the United States in 2008 was 40,100, with 7,470 deaths from this disease [1]. The majority of patients diagnosed with uterine cancer are diagnosed at an early stage (FIGO stage I), when surgical resection often leads to a good prognosis [2]. While hysterectomy and bilateral salpingo-oophorectomy are the standard of care for stage I tumors, the role for lymphadenectomy is still highly debated. This is due to the fact that there are significant risks associated with this procedure, including increased operative time and surgical complications, lymphedema, and lymphocyst formation [3]. Furthermore, evidence suggests that lymphadenectomy for stage I disease affords no improvement in overall or recurrence free survival [4]. Nonetheless, approximately 10% of women with stage I disease will have metastases to the pelvic lymph nodes, a finding which changes both the treatment recommendations and prognosis for the patient [5].

For this reason, SLN sampling is a surgical procedure that has gained enthusiasm as a means of identifying those patients who should be upstaged. This technique has been shown to be more accurate than MRI or CT scan [6], but without the risks associated with complete lymphadenectomy [7].

In higher risk disease (both higher stage as well as for tumors with intermediate risk factors), the role of SLN biopsy also remains unclear. While lymphadenectomy remains the standard of care in this patient population, SLN biopsy may be useful in patients who either refuse lymphadenectomy or for those patients who are unable to undergo this procedure due to surgical risk factors.

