2.2 Secondary Objective(s)

To compare different surgical modalities (open procedures, minimally invasive procedures, and single-site technology) and different injectants (isosulfan blue and indocyanine green) for SLN biopsy.

To determine total operating room time (from the time the patient enters the room to the time the patient leaves the room) as well as console time (robotic)/ operating time for minimally invasive procedures.

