The procedural and SLN variables will be collected at the time of the procedure. The procedural variables that will be collected will include: surgical modality, total operating room time, console time (robotic)/SILS operating time, time from cervical injection to SLN inspection/detection, estimated blood loss, intra-operative complications, conversion to laparotomy (for MIS) (Figure 2.)

Figure 2. Data Collection Sheet: Procedural Variables

Patient ID	Surgical modality	Total OR time	Console/ SILS operating time	Injection – SLN detection	EBL	Complications	Conversion

The console time/ operating time (for MIS procedures) will be documented from the time that the sentinel lymph node dissection begins and include the SLN biopsy, the hysterectomy, bilateral salpingo-oophorectomy, and complete lymph node dissection. All procedural variables collected will be documented at the time of surgery by either the Gynecologic Oncology fellow or the attending surgeon. Pathologic variables will include: the number of SLN detected on each hemipelvis (both by isosulfan blue and by ICG), location of mapped SLNs, number of positive lymph nodes (both SLN and in full lymphadenectomy), total number of pelvic lymph nodes dissected, total number of para-aortic lymph nodes dissected, histologic subtype, depth of myometrial invasion, grade, tumor size, lymphovascular space invasion, final stage of disease.

Reported adverse events and potential risks of Isosulfan Blue and Indocyanine Green are described in Section 7.0.

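### The optional multivariable model takes true nodal metastasis as its outcome, so its dye, modality and surgeon terms cannot measure SLN performance; its stage term may also restate the outcome

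*Combined protocol and SAP*

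**What the plan says.** Section 12.0, in its opening paragraph and ahead of the four specific aims, allows as an optional secondary analysis a "logistic regression using metastasis as the dependent variable with type of dy utilized, surgical modality, surgeon, tumor stage, grade" and lymphovascular space invasion as the predictors. No SLN result, SLN detection or false-negative term appears in the model.

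The same section shows what metastasis means. The aims concern the "negative predictive value of SLN biopsy for detecting metastasis", so metastasis is the target condition and not the test result. Section 10.1 agrees, describing "the sensitivity of the sentinel node to determine the true lymph node status (metastatic disease or not". Section 6.2 establishes that status by a complete pelvic lymphadenectomy after SLN removal, whichever dye or modality is used, and leaves the choice of modality to the surgeon.

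On stage, the pathologic variables listed in section 6.2 end with "lymphovascular space invasion, final stage of disease". No pre-operative stage is on the collection list. Section 1.1 presents SLN sampling as a means of "identifying those patients who should be upstaged".

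The secondary objective in section 2.2 is "To compare different surgical modalities (open procedures, minimally invasive procedures, and single-site technology) and different injectants".

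**The concern.** Dye, modality and surgeon are the technique variables of interest, and this is the only adjusted analysis in the plan. Specific Aims 2 and 3 are unadjusted two-sample tests on groups that were not randomised. A reader wanting an adjusted answer to the secondary objective will look at this model.

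Whether a woman's nodes contain tumor is settled before the operation. A technique can find or miss that disease but cannot create it. With metastasis as the outcome, a significant dye term would mean that one dye was used in women more likely to be node-positive, or that their nodes were dissected more completely. It could easily be reported as a difference in technique. Conversely, a real difference in SLN accuracy would not show.

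The stage term raises a separate problem. If it is final stage, it is assigned after nodal pathology is known and therefore carries part of the outcome into the predictors.

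**Working it through.** **1. The plan's own figure.** Section 3.2 gives a 5% margin E, 95% confidence, population N = 20,000 and p = 0.15. With x = z²p(1−p) = 1.96² × 0.15 × 0.85 = 0.490, n = Nx / ((N−1)E² + x) = 9,796 / (50.00 + 0.49) = 194.0, so 195. The stated 200 is within 3% of that. It is a precision calculation for one proportion and does not size any regression. Expected node-positive women are 200 × 0.09 = 18 to 200 × 0.13 = 26 at the two rates cited there, or 30 at the cautious 15%.

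**2. The outcome.** Let a dye group have node-positive rate p and SLN sensitivity s. With complete dissection, the proportion recorded as metastatic is ps (found by the SLN) + p(1−s) (found only in the remaining nodes) = p. Sensitivity cancels. The dye odds ratio is therefore [p₁/(1−p₁)] / [p₀/(1−p₀)].

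- *Real performance difference, same case mix.* Assume sensitivities of 95% and 70%. The sensitivity odds ratio is (0.95/0.05) / (0.70/0.30) = 8.1. With p₁ = p₀, the dye odds ratio for metastasis is 1.00. Simulating 200 women at 13% node-positive, with two dyes 1:1, gave a significant dye term in 3.8% of 1,000 trials, no more than the 5% error rate.
- *Same performance, different case mix.* With p₁ = 0.13 and p₀ = 0.09 (rates borrowed from section 3.2 for illustration), the odds ratio is (0.13/0.87) / (0.09/0.91) = 0.1494 / 0.0989 = 1.51.
- *Incomplete dissection.* Section 6.2 allows the procedure to be varied, and Appendix A calls the lymphadenectomy possible where section 4.1.3 does not. If only a fraction c of the remaining disease is found, the recorded rate is p[s + (1−s)c]. This mixes prevalence, sensitivity and completeness, and cannot be read as any one of them.

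**3. The stage term, read as final stage.** Suppose every node-positive woman leaves the early stages, and stage is entered as early versus advanced. The early-stage group then has no events. Its log-likelihood contribution keeps rising towards zero as the intercept falls, while the stage coefficient rises to compensate. There is no finite maximum-likelihood estimate for stage, and in the limit the other coefficients are estimated from the advanced-stage women alone.

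Illustration with assumed counts (n = 200):

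| | Node-negative | Node-positive |
|---|---|---|
| Early stage | 171 | 0 |
| Advanced stage | 10 | 19 |

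The model was fitted to this table 300 times with randomly assigned binary dye and grade. The fit failed numerically in 75 runs. In the rest the stage coefficient ran off to a median of about 29 on the log-odds scale, and the dye coefficient equalled that from the 10 + 19 = 29 advanced-stage women. One such fit gave a dye coefficient of −0.51 with standard error 0.82. A 95% interval then spans a factor of exp(1.96 × 0.82) ≈ 5 either side of the odds ratio.

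The result depends on coding. With stage scored 1 to 4 and a few node-negative women assumed at stage 4, the model converged (stage coefficient 3.1, standard error 0.66).

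**4. Room for a replacement model.** Section 1.3 reports detection rates of 78% (meta-analysis) and 89-95% (later prospective studies). Non-detections in 200 women are 200 × 0.05 = 10 to 200 × 0.22 = 44. Three dye levels (2 parameters), three modality groups (2) and one continuous case-mix variable (1) make 5 parameters, or 10/5 = 2.0 to 44/5 = 8.8 events per parameter.

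**The case against.** The strongest reply is that section 12.0 never says this model describes SLN performance. It is worded as something the analysis may include and sits outside the specific aims. The secondary objective is handled in Aims 2 and 3, which compare sensitivity, specificity and NPV directly. All of that is true, and it limits the consequences. It does not rescue the model. If the purpose is to study risk factors for metastasis, then dye, modality and surgeon do not belong in it, and neither section 2.1 nor section 2.2 asks for such a model.

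On stage, the objection partly succeeds. Section 12.0 does not define tumor stage. Section 1.1 speaks of nodal metastases in about 10% of women with stage I disease, and section 3.2 cites node-positivity in presumed stage I-II disease. Both use stage in a sense that precedes nodal findings, and under that usage early-stage women do have events. A reader might infer that the circularity is certain. The documents do not support that, because they state neither which stage is meant nor the boundary that upstaging crosses. The list in section 6.2 still leaves a problem either way: the term is final stage, or it is a variable that is not on the collection list.

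A reader might also infer that the whole model must break down. It need not. Even with complete separation on stage, the dye coefficient is finite in most fits, and with other codings of stage the fit converges. The defect is a stage estimate that may not exist and other estimates that rest on few women.

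**Conclusion.** As written, the model answers the wrong question for its technique variables. This follows from the plan's own use of metastasis as the true nodal status, and holds however stage is defined. A sensitivity odds ratio as large as 8.1 would leave no trace in the dye term, while a case-mix difference of 9% against 13% would produce an odds ratio of about 1.5. The sensitivities and the split of rates between dyes are illustrative assumptions; the cancellation of sensitivity assumes complete dissection.

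The circularity is conditional on three things: tumor stage being final stage, node-positive women all moving out of the early stages, and an early-versus-advanced coding. Under those conditions stage has no finite estimate and the remaining terms depend on the advanced-stage women only.

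It would be going too far to conclude that the trial's main results are affected. The model is optional, and the estimates in Aims 1-4 do not use it. The sentence should be corrected before analysis because it would supply the only adjusted results on dye and modality.

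**What to change.** Rewrite the sentence in section 12.0 as follows.

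- **Outcome:** SLN detection, yes or no per woman, stating how a woman mapped on one hemipelvis only is counted. Detection comes first in the primary objective (section 2.1), yet section 12.0 names no analysis of it.
- **Dye:** three levels (isosulfan blue, ICG, both), because section 6.2 allows either or both in one woman.
- **Stage:** remove final stage.
- **Predictors:** prespecify only dye, modality and one or two case-mix variables already collected, such as grade or tumor size. With about 10-44 non-detections expected, a longer list is not supportable. Surgeon may well matter for detection, but terms for individual surgeons would probably have to be left out. At the 95% detection end even the short model is thin and should be labelled exploratory.

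The change costs one sentence and needs no new data. There are two downsides. The metastasis risk-factor model, which is not a stated objective, is given up. Detection also says nothing about missed disease, so the sensitivity and NPV comparisons in Aims 2 and 3 stay unadjusted and should be reported as such.
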